Exclusion criteria: Patients with clinical evaluation of high-risk pregnancies will be excluded, including chronic hypertension, diabetes mellitus, obesity, multiple pregnancies, severe COVID-19 infection, previous thromboembolic event, acute or chronic hematological events (eg, thrombus formation isolated to thrombophilia), use of anticoagulants, cardiovascular disease, lung disease, kidney disease, immunosuppression, severe mental disorder, recurrent abortion, previous premature birth, previous or current cancer.

Sample size and power calculation

The sample size calculation was based on the primary outcome - difference between scores on the GAD-7 anxiety scale -, compared to means, estimated at 4 points, and standard deviation of 4 points. A sample of 26 patients each group is needed to have 80% power, at the 5% significance level; considering losses of 15% in the follow-up, the final size of the intended sample will be 60 patients. Recruitment will continue until target sample size is reached. The sample was calculated using the formula for superiority randomized clinical trials proposed by WANG et al., 2017 (Figure 1):

$$n_1 = \left\lceil \frac{(z_\alpha + z_\beta)^2 (\sigma_1^2 + \sigma_0^2 r)}{(d - \delta)^2} \right\rceil,$$

$$n_0 = \left\lceil \frac{(z_\alpha + z_\beta)^2 (\sigma_1^2 / r + \sigma_0^2)}{(d - \delta)^2} \right\rceil.$$

Figure 1: formula for superiority randomized clinical trials.

Recruitment

The recruitment population includes pregnant women presenting for their first antenatal visit at 6 to 12 weeks of gestation. Participation in the study will be followed until completion of the postpartum period.

Eligible participants will receive information about study design, objectives, risks and benefits in adapted language, participant information leaflet and participant consent form (Appendices).

Randomisation

The randomization process in this RCT will use random permuted blocks to ensure similar numbers of participants in each intervention arm throughout the trial and

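### Sixty women with 15% lost leave 51, one short of the 52 the plan requires; 60 covers losses of about 13%

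*Combined protocol and SAP*

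**What the plan says.** All the figures are in the section on sample size and power calculation. The requirement is "A sample of 26 patients each group is needed to have 80% power, at the 5% significance level". Allocation is 1:1 (opening of the design section), so this means 52 women with outcome data. The same sentence goes on: "considering losses of 15% in the follow-up, the final size of the intended sample will be 60 patients". It does not show how the 15% was turned into 60.

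On recruitment, the section says: "Recruitment will continue until target sample size is reached". Neither this section nor any other gives a rule for replacing women who are lost.

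The inputs behind the 26 are a GAD-7 difference "compared to means, estimated at 4 points" and a "standard deviation of 4 points".

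**The concern.** An allowance for losses is meant to ensure that the required number remains after the expected proportion has gone. Losses occur among the women enrolled, so the enrolled number has to be the requirement divided by the proportion retained. Here the enrolled number, the loss rate and the requirement are all stated, and the first two do not return the third.

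Little is at stake for the trial's ability to answer its question. The point concerns a stated sample-size figure that fails a one-line check, in a plan that commits to CONSORT reporting. It can be put right before recruitment, which the trial status section places after ethics approval.

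**Working it through.** **Inputs** (section on sample size and power calculation, unless noted)

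- Required: 26 per group, so 2 x 26 = 52.
- Losses: 15%.
- Stated final size: 60.
- Allocation: 1:1 (design section).
- Difference 4 points, SD 4 points, 80% power, 5% significance. Sidedness and the superiority margin in the formula are not given values; I take a margin of zero unless noted.

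**Step 1. Reproduce the stated 60.** Requirement x (1 + loss) = 52 x 1.15 = 59.8, rounded up to 60. Per group, 26 x 1.15 = 29.9, rounded up to 30. Both match the plan.

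**Step 2. Check what 60 delivers.** 60 x (1 - 0.15) = 51.0, or 25.5 per group. This is one below 52.

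**Step 3. Find the loss rate that 60 covers.** 1 - 52/60 = 8/60 = 13.3%.

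**Step 4. Find the size that covers 15%.** 52/(1 - 0.15) = 61.2. Sixty-one women leave 61 x 0.85 = 51.85, still short. Sixty-two (31 per group) leave 62 x 0.85 = 52.7, which is enough.

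**Step 5. Effect on power** (two-sample t-test, two-sided 5%)

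| Assumption | 26 + 26 | 25 + 26 | Change |
|---|---|---|---|
| Stated inputs: difference 4, SD 4 | 94.2% | 93.8% | 0.4 points |
| 26 per group gives exactly 80% (difference about 3.17, SD 4) | 80% | 79.2% | 0.8 points |

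**Step 6. Check the base of 26.** With zero margin and equal SDs, the plan's formula reduces to n per group = 2(z_alpha + z_beta)^2 x SD^2/difference^2.

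- Two-sided 5%, 80% power: 2 x (1.960 + 0.842)^2 x 16/16 = 15.7, so 16 per group (17 by the t-test).
- One-sided 5%, 80% power: 2 x (1.645 + 0.842)^2 x 16/16 = 12.4, so 13 per group, or 26 in total.
- Two-sided 5%, 95% power: 2 x (1.960 + 1.645)^2 x 16/16 = 26.0, so 26 per group.

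At 80% power, 26 per group would also arise from a difference of about 3.1 points, or from an unstated margin of about 0.85 points (two-sided) or 1.2 points (one-sided). The documents do not say which, if any, was used.

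This bears on the remedy. If the reconciled requirement were 17 per group, for example, then 34/0.85 = 40 and 60 would be more than enough.

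**The case against.** Several stronger readings are tempting, and the documents do not support them.

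- **That the authors are shown to have multiplied by 1.15.** The match in Step 1 makes this likely, but no inflation step is written down, and choosing a round 30 per group would also give 60. The shortfall in Step 2 does not depend on how 60 was reached. Part of the two-woman gap between 60 and 62 is also rounding up to equal groups.
- **That recruitment stops at exactly 60.** The text says only that it continues until the target is reached. That does not rule out a small overrun, but none is promised.
- **That exactly 51 women would enter the primary analysis.** Figure 2 schedules GAD-7 at four time points from the first trimester to the puerperium, and the analysis plan uses a mixed model or GEE under intention to treat. A woman lost late may still contribute data. This softens the consequence, but the sample size was set by a comparison of two means with its own explicit loss allowance. The analysis plan also does not name the time point of the primary contrast. Multiple imputation is described in the economic paragraph, so I do not rely on it here.
- **That the trial is underpowered or must enrol 62.** Steps 5 and 6 give no support for either.

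The most direct defence is that 15% was meant as a share of the 52: 0.15 x 52 = 7.8, about 8 women, and 60 - 8 = 52. The arithmetic then closes. But losses in follow-up are ordinarily counted among those enrolled, and 8 of 60 is 13.3%. If this was the intention, the sentence should say so, and the correction below does that.

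**Conclusion.** The point holds as a small inconsistency: at 15% losses the stated 60 leaves one woman fewer than the plan's own 52, and 60 covers losses of 13.3%. It rests on reading the 15% as a share of the women enrolled and on taking the plan's 26 per group at face value. It does not rest on any view of how 60 was calculated.

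The effect on power is 0.4 to 0.8 percentage points, and women lost late may reduce it further by contributing repeated measurements. A reader might infer that the target should rise to 62. The documents do not support that, because 62 is right only if 26 per group is right, and 26 does not follow from the stated difference, SD, power and significance level with zero margin. Reconciling the 26 is the larger question and should come first. This is a correction of wording at the lowest level of importance.

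**What to change.** Keep 60 and change one clause in the section on sample size and power calculation, to say that 60 women (30 per group) allow for losses of up to about 13% of those enrolled. This costs one sentence and no extra women.

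If the 26 per group is first reconciled with its inputs (sidedness, margin, power and difference all stated), apply the allowance to the reconciled total as n/(1 - 0.15), round up to equal groups, and show the step. That gives 62 only if 26 stands. The best course is to make both corrections together, before recruitment starts.

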Four categories of costs will be collected: (1) Intervention costs and usual care costs, (2) Healthcare costs (i.e., medication costs, primary, secondary, and tertiary costs), (3) Informal care costs (i.e., transportation costs, caregiver costs, internet costs), and (4) Lost productivity costs. Intervention costs will be calculated using a bottom-up approach in which the resources consumed by the intervention will be collected (i.e., minutes spent in the teleconsultation by the obstetrician). Costs related to the use of health services (i.e., healthcare costs) and costs incurred by the patient and family (i.e. informal care costs) will be measured using an adapted version of questionnaires developed by Vidal and collaborators (16) and by researchers of the Stringer study (17) (Chart 4). Lost productivity costs (i.e., absenteeism from work and presenteeism) will be measured using an adapted version of the iProductivity

Cost Questionnaire (iPCQ) developed by researchers of the Institute for Medical Technology Assessment (iMTA) (18). All costs will be measured at prenatal trimestral appointments and will cover the period between appointments (i.e., 3 months). Costs will be evaluated according to the to the Brazilian Public Health reimbursement table of Sistema de Gerenciamento da Tabela de Procedimentos, Medicamentos e OPM do SUS (SIGTAP)(19), to the Instituto Brasileiro de Geografia e Estatística (IBGE)(20).

Chart 4: Costs related to prenatal care.

Estimated personal costs for adherence to prenatal care		
Work	Current job	Describe
	Job loss due to pregnancy?	Yes or No
	Do you have regular employment?	Yes or No
	Do you have leave for medical appointments?	Yes or No
Transport	Working time lost to attend the medical appointments	In hours
	Means	On foot, municipal van, bus, app, own vehicle
	Cost	In Reais
Children under guardianship	Time	In minutes
	Children under 12 years old in their responsibility	Quantity
	Do they need to stay with a caregiver for the medical appointment?	Yes or no, estimated cost in Reais
Companion	Do they attend daycare or school? Public or private?	Yes or no, estimated cost in Reais
	Does a partner or family member need to miss work to accompany you to medical appointments?	Yes or no, estimated cost in Reais
	Do you have a computer with internet at home?	Yes or No
Telemedicine	Do you have a cell phone with internet access?	Yes or No
	Estimated monthly cost for internet access/hour	In Reais

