This RCT will have an analysis by intention-to-treat and per protocol (at least 6 sessions attended) since it is an RCT of effectiveness. The primary outcome will be analyzed by generalized linear models of mixed effects (GLMM) or by generalized estimation equations (GEEs). Adjustments for confounding or baseline variables may be made if justified. Secondary outcomes can be analyzed in 2-test linear models using the Mantel-Hanszel test, linear trends for ordinary categorical variables or multivariate regression models for categorical variables. For repeated measures, the same analysis of the primary outcome (GLMM or GEEs) will be maintained. The

level of significance for the statistical tests conducted will be 5% and effect estimates will be presented with 95% confidence intervals.

The cost-effectiveness and cost-utility analysis will be carried out following the intention-to-treat principle according to the randomized clinical trial dataset (22) in software R. The differences in cost and effect will be estimated using a set of equations of apparently non-correlated regressions, which adjusts the model to correlate costs and effects and also allows adjustment for potential confounding factors. The incremental cost-effectiveness ratio (ICER) will be calculated by dividing the difference in costs between interventions by the difference in effect between interventions. Bias-corrected accelerated bootstrapping with 5000 replications will be used to estimate uncertainty around costs and effects. The cost-effect pairs, results of 5000 bootstrapping replications, will be plotted in cost-effectiveness plans (CE-plan) (23). The cost-effectiveness acceptability curves (CEACs) will be estimated to show the probability that the intervention will be cost-effective compared to the control, in different amounts of willingness to pay (that is, the amount in Reais that the health system is willing to pay per unit of effect won) (23). Multiple imputation will be used to predict missing data. The data imputation model will include variables associated with the missing data (24).

Data protection and participant confidentiality

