In the scenario of uncertainty of COVID-19 pandemic and in consonance to principle of non-malfeasance, pregnant women were recommended to carefully follow the non-pharmacological countermeasures, such as social distancing, hand hygiene and use of masks, restricting themselves to leave home only for prenatal appointments and to perform complementary tests - which, paradoxically, became potentially a risk event. Some pregnant women did not attend medical appointments, especially in developing countries; as a consequence, screening for gestational risk factors was hampered (5). Maternal-fetal care is essential. Pregnant women who do not attend antenatal services are at increased risk of maternal death, unfavorable perinatal outcomes, and stillbirth. There is evidence of a difference in stillbirth incidence between the pre-pandemic and pandemic period reporting 9.31/1000 live births versus 2.38/1000 live births, $p = 0.01$), showing a marked increase in the number of stillbirths in the pandemic transition. The adoption of health care models that include telemedicine is still a challenge in middle-income countries; however, it is of fundamental importance in expanding access and reduces infant and maternal morbidity. Despite the pandemic, pregnant women need to follow up on prenatal

care; even if barriers imposed by the situation have to be overcome or new approaches to care have to be taken (26).

Evidence on the impact of the number of antenatal visits on maternal and fetal outcomes is limited; similarly, while some studies point to reducing the number of visits, home care, and group care as safe, robust clinical trials with comparative results are not available (27). A systematic review by Villar concluded that, for usual-risk pregnant women, a reduction in the number of consultations does not imply worse maternal-fetal outcomes. Similarly, a study by Partridge demonstrated that fewer than 10 prenatal visits were not associated with worse fetal outcomes such as low APGAR, ICU admission, and neonatal death (28).

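### Questionnaire-based costs have no collection route when a trimestral appointment is missed, so the incremental cost and ICER may be biased in an unknown direction

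*Combined protocol and SAP*

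**What the plan says.** The cost paragraph under Outcome variables lists four categories: intervention and usual-care costs, healthcare costs, informal-care costs and lost productivity. Healthcare and informal-care costs come from adapted questionnaires (Chart 4), and lost productivity from an adapted productivity questionnaire. On timing it says "All costs will be measured at prenatal trimestral appointments and will cover the period between appointments", with an interval of three months. No telephone, online or record-based route is described for a woman who misses that appointment.

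Intervention costs have a different source: "Intervention costs will be calculated using a bottom-up approach in which the resources consumed by the intervention will be collected". Figure 2 places implementation costs at finalization.

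Several Chart 4 items are driven by visits: transport, child care, a companion's absence from work, and "Working time lost to attend the medical appointments".

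For gaps, the Analysis plan says "Multiple imputation will be used to predict missing data". It adds that the model will use variables related to missingness, but does not list them. Arm, attendance and emergency use are not named. Under Outcomes, attendance and extra obstetric-emergency consultations are recorded as measures of adherence. Nothing links them to costing or to the imputation.

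**The concern.** Cost data are gathered at the event whose delivery the trial changes. Usual care has at least 9 appointments, all in person; telemedicine has at least 6 in person and 3 online. A missed trimestral appointment can lose three months of questionnaire-based costs, and the reason it was missed may be related to those costs. A visit that did not happen incurs no fare, child care or lost working time, so predicting these from women who completed the questionnaire can add spending that never occurred. In the other direction, a woman who stays away may use emergency care more. The Discussion notes that "Some pregnant women did not attend medical appointments, especially in developing countries", so missed appointments are not a remote possibility.

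At stake are the incremental cost, the ICER and the acceptability curve. The economic analysis is a named secondary outcome, and reduced cost is one of the stated aims of the hybrid model.

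**Working it through.** The documents give no cost, cost SD, or attendance rate by arm, so there is no plan figure to reproduce. The only related number is a 15% loss to follow-up in the sample-size section, which is neither by arm nor per cost interval. All values of p and r below are assumptions.

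**1. Formula.** Let p be the share of intervals missing in an arm, and r the true cost of a missed interval divided by its imputed cost. Take the imputed cost as 1.0 in both arms. The error in the telemedicine-minus-usual-care difference is

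bias = p_T(1 − r_T) − p_U(1 − r_U).

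A negative value makes telemedicine look cheaper than it is.

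**2. Is unequal attendance enough?** No. With r = 1 in both arms, the bias is 0 at every pair tried (telemedicine/usual care 15/15, 10/20, 5/25 and 0/30% missing).

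**3. Is it necessary?** No. With 15% missing in both arms, r_T = 0.5 and r_U = 1.5, bias = 0.15 × 0.5 − 0.15 × (−0.5) = +0.15, or +15%.

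**4. Illustrative size.** Assume p_U of 15-25%, p_T of 5-10%, and the same r in both arms, so bias = (p_T − p_U)(1 − r).

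| Missing, telemedicine / usual care | r = 0.6 | r = 1.5 |
|---|---|---|
| 10% / 15% (smallest gap) | −0.05 × 0.4 = −2% | −0.05 × (−0.5) = +2.5% |
| 5% / 25% (largest gap) | −0.20 × 0.4 = −8% | −0.20 × (−0.5) = +10% |

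**5. Can imputation remove it?** This was simulated with regression-based multiple imputation: 4000 women, 60 repetitions, 5 imputations, about 5% missing in telemedicine and 25% in usual care. The cost base was 100 and the arm difference −20 before any change to missed intervals.

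| Situation | Bias (base 100) |
|---|---|
| Missing at random, arm and attendance predictor in the model | −0.07 (Monte Carlo SE 0.05) |
| Missing at random, predictor left out | −3.5 |
| Missing at random, arm left out | +4.0 |
| Missed intervals at half cost, both in the model | −10.4 |
| Missed intervals at 1.5 times cost, both in the model | +10.4 |

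A well-specified model is unbiased when missingness is explained by what it contains. It does not repair a cost gap that goes with the missed interval itself.

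**6. One visit is not one interval.** Nine appointments spread evenly over three trimesters is 9/3 = 3 per interval. If one is missed, visit-driven items fall to about 2/3 of their usual level, not to zero. Medication, other healthcare, internet and presenteeism costs do not depend on that visit. For a woman who missed only that one visit, r would therefore be above 2/3 unless her other costs also differ.

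**The case against.** Four stronger readings are tempting, and the documents support none of them.

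- *The cost difference is biased whenever attendance differs by arm.* Steps 2 and 3 show that this is neither sufficient nor necessary. Nor do the documents predict different attendance: both arms have at least 6 in-person visits, and the Discussion remark concerns pandemic access in general.
- *A missed visit simply receives an attender's cost.* The Analysis plan promises a model using variables related to missingness, so imputation is conditional and can be unbiased. Attendance and emergency use are recorded and could enter that model.
- *A missed appointment makes the interval's visit costs zero.* Step 6 shows otherwise.
- *Every cost category is lost.* Intervention costs are counted bottom-up, and implementation costs are placed at finalization.

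It can also be said that nothing forbids giving the questionnaire at the next visit, and that the possible bias is small beside sampling error. Assuming a cost coefficient of variation of 0.5 to 1.0 and 30 women per arm, the standard error of the difference is CV × √(2/30), about 13% to 26% of the mean. The economic analysis is secondary, and the Background describes the study's objective as feasibility.

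These points limit the size and importance of the concern. They do not supply the missing rule. Collecting at the next visit is allowed by silence, not planned. A systematic error shifts the centre of the bootstrap cloud and the acceptability curve, and the interval width does not reveal it. The imputation model remains unspecified where specification matters, as the simulation shows.

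**Conclusion.** The concern holds in a limited form. Healthcare, informal-care and lost-productivity costs are tied to prenatal trimestral appointments, with no stated route when one is missed and an unspecified imputation as the only remedy. The incremental cost and ICER *may* be biased, if missed intervals differ in cost from what is imputed by an amount or frequency that differs between arms.

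The step 4 range, up to 8% of mean interval cost in one direction and 10% in the other, rests wholly on the assumed missing shares and on r of 0.6 or 1.5. It is an illustration, not a forecast. The sign is unknown, because avoided visit costs and extra emergency use pull in opposite directions. That favours collecting the data over correcting for their absence later. This is a worthwhile, inexpensive improvement to a secondary analysis, and it does not bear on the GAD-7 primary outcome.

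**What to change.** In the cost paragraph under Outcome variables:

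- Give the cost questionnaires to every randomised woman at each trimester time point, whether or not she attended. After a missed appointment, use telephone, video, an online form or the next contact, within one stated window that is the same in both arms.
- Take the number and mode of visits from the attendance records already kept for adherence. Apply transport, companion, child-care and lost-work costs only to visits that took place, so that each missed visit counts as zero, but not the whole interval.

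In the Analysis plan:

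- Impute only what is still missing, and name arm, attendance and emergency use among the variables in the imputation model.

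The cost is a few extra calls by data collectors who are already to be trained. Some questionnaires will be answered remotely rather than face to face, a small downside. The change should be made before recruitment, since costs not collected at the time cannot be reliably recovered.

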
BACKGROUND

COVID-19 is a viral infection caused by SARS-CoV-2, which spreads primarily via respiratory droplets during close face-to-face contact (1). Pregnant women are known to be disproportionately affected by respiratory illnesses, which are associated with increased infectious morbidity and high maternal mortality rates (2). In this scenario, many expecting mothers are unable to visit the clinician or health center, especially in developing countries; this might lead to missing out on high risk factors in due course of pregnancy (3). Remote care enables a provision of obstetric care at contingency plans, in order to minimize antenatal visits, as it limits an exposure to SARS-CoV-2 for healthy pregnant women and also for healthcare providers (4). Telemedicine can potentially mitigate potential adverse effects of reduced antenatal visits. Several studies have shown that telemedicine is an effective strategy, in which applying evolving telemedicine capabilities can improve good quality care for obstetric patients (5). A systematic review suggests that obstetrical telemonitoring has a great potential for contributing with better gestational outcomes, early detection of complications, prevention of intercurrences, and providing rapid intervention even before hospitalization (6). Some studies suggest that reduced-frequency prenatal care model, technology-enhanced, is as safe as the standard model of care for low-risk pregnant women (7). Although, there is low-grade evidence published, Brazil has an incipient regulation of telemedicine and, therefore, most prenatal care has been conducted face-to-face. Here we describe a research protocol of a study whose objective is to assess the feasibility of conducting a randomized controlled trial on the effectiveness and the cost-effectiveness of prenatal care telemedicine. The null hypothesis to be tested in this study is that

there is no difference in (cost-) effectiveness on maternal health outcomes between patients undergoing standard prenatal care compared to those receiving telemedicine for prenatal care.

METHODS/DESIGN

Unblinded, parallel group, randomized controlled trial

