Data collection has four components: baseline demographic characteristics, quality of life and economics data, anxiety scores and clinical outcome data. Undergraduate medical students and Gynecology and Obstetrics residents, trained in conducting diagnostic assessments, will collect data and apply the standardized questionnaires. In order to compare participants in both arms, data on clinical risk factors and socioeconomic status will be collected during the recruitment phase, using the baseline characteristics questionnaire (Table 1).

Chart 1: Baseline characteristics questionnaire

	Variable	Description or Categories
Demographic characteristics	Distance from capital	In kilometers (km)
	Age	In years
	Skin color	White, black, asian, brown, indigenous
	Marital status	Single, married/living together, separated/divorced, widowed
	Scholarly	Elementary, high school, youth and adult education, higher education
	Occupation	Currently performed job
	Work situation	Employee with a formal contract, employee without a formal contract, civil servant, self-employed, unemployed
	Working hours per day	In hours
	Income	In Reais
	People living on this income	01, 01 to 03, 04 or more
Clinical characteristics	Children who live on this income	01, 02, 03, 04 or more
	Weight at 1st medical appointment	In kilograms (Kg)
	Height	In centimeters (cm)
	Blood pressure at 1st medical appointment	In millimeters of mercury (mmHg)
	Prior parity	Number of pregnancies, abortions, childbirth, cesarean sections, molar and ectopic pregnancies
	History of premature birth or stillbirth	Yes or no
	Comorbidities	Describe chronic diseases
	Chronic use medications	Describe medications in use

Outcome variables

Severity of anxiety among pregnant women and postpartum women will be evaluated by GAD-7 scale (Chart 2), which has been validated for assessing anxiety

in pregnant women, in a study developed by Zhong and collaborators (13). This scale had good reliability, internal and external validity; patients with scores greater than or equal to 07 required careful follow-up (13).

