Clinical outcomes will be collected to explore the clinical effectiveness of the TPC based on hospital database reviews (Chart 5).

Chart 5: Maternal-fetal outcome and puerperal aspects

Maternal-fetal outcome and puerperal aspects	
Delivery methods	Vaginal or cesarean
Gestational age at birth	preterm, term, post term
Maternal complication	Infectious, hemorrhagic, none, other
Newborn's size	Small, appropriate, large for gestational age
Need for neonatal ICU	Yes or No
Breast-feeding	Yes or No; time and reason
Need to return to obstetric emergency	Yes or No; reason
Need for medical appointments in pediatric emergency	Yes or No; reason

Outcomes

Primary outcome: Mean between-group differences in GAD-7 scores.

Secondary outcome 1: difference between means, between groups, of data related to the mother: delivery mode and obstetric complications.

Secondary outcome 2: difference between means, between groups, of data related to the baby: gestational age at birth, birth weight, APGAR, neonatal intensive care unit (ICU) admission.

Secondary outcome 3: economic analyses.

The quality of assistance will be evaluated by the Humanization Program for Prenatal and Birth (PHPN) criteria proposed by Brazil Ministry of Health (21). Adherence to the proposed care will be assessed by attending the consultations, carrying out the proposed exams and extra consultations in the Obstetric Emergency. The schedule intervention was present at Figure 2.

Figure 2: Flow Chart of recruitment, intervention and evaluations

Figure 1: Flow Chart of recruitment, intervention and evaluations								
MOMENT	Study period							
	Screening	Allocation	Post Allocation				Finalization	
-t1	0		t1	t2	t3	t4	t5	t5
RECRUITMENT								
Eligibility evaluation	X							
ICF *		X						
Allocation		X						
INTERVENTION								
SG and GC: In-person queries			X	X	X	X		
SG: Telemedicine consultations			X	X	X	X		
EVALUATION								
Sample ascription	X							
Anxiety (GAD-7)			X	X	X	X		
LQ and costs (E5-5D)			X	X	X	X		
Personal costs								
Implementation costs							X	
Clinical Outcomes							X	
Feasibility								X
Accession								X
Quality (PHN)								X
Cost-effectiveness								X

Legend

t1 Initial eligibility evaluation through referral to the PN
 T0 Allocation based on eligibility criteria
 t1 First Trimester
 t2 Second trimester
 t3 Third trimester
 t4 Puerperium

Analysis plan

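### No GAD-7 or EQ-5D is scheduled before allocation in this unblinded trial, so no pre-allocation score is available for adjustment, and the role of t1 is not stated

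*Combined protocol and SAP*

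**What the plan says.** Methods/Design describes an "Unblinded, parallel group, randomized controlled trial". The Outcomes section gives the "Primary outcome: Mean between-group differences in GAD-7 scores", with no visit and no reference to a baseline value.

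In Figure 2, the GAD-7 row and the row labelled "LQ and costs (E5-5D" each carry four marks. These fall in the same four columns as the in-person and telemedicine consultations. Consent and allocation are marked in an earlier column, and the screening column holds only the eligibility check and the sample ascription. The legend gives "T0 Allocation based on eligibility criteria" and "t1 First Trimester" and says nothing more about either time point.

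Variables and data collection states: "In order to compare participants in both arms, data on clinical risk factors and socioeconomic status will be collected during the recruitment phase". The instrument for this is Chart 1, which lists demographic and clinical items but neither GAD-7 nor EQ-5D.

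The Analysis plan leaves adjustment for baseline variables optional and names none. It does not say which of t1 to t4 enter the primary model as outcomes. The cost-utility regressions also allow adjustment, again without naming a covariate.

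**The concern.** A score taken before allocation cannot be affected by the arm, and it is often the strongest available predictor of later scores on the same scale. Without one, the trial gives up whatever precision that predictor would bring to its 95% confidence intervals. It also cannot show whether the arms began with similar anxiety.

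The unstated role of t1 adds a second question. Women enrol at 6 to 12 weeks, so allocation and the first-trimester assessment can fall close together. An analyst looking for a baseline may reach for t1. Because the trial is unblinded and the scale is self-rated, a t1 score given by a woman who knows her arm may already have moved, and adjusting for it would then remove part of the effect. Data collected after allocation cannot show whether this has happened.

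**Working it through.** **Inputs.** From Sample size and power calculation: a difference "estimated at 4 points, and standard deviation of 4 points", and "A sample of 26 patients each group is needed to have 80% power, at the 5% significance level". The documents give no between-visit correlation, so I assume ρ = 0.3, 0.5 and 0.7 under two structures: equal between all visits, or decaying with visit distance (AR(1)). Complete data are assumed. No contrast is named, so the mean of t2–t4 is used for illustration, with a pre-allocation score one visit-step before t2.

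**The plan's own figure.** With a margin of zero and a two-sided test, n = 2(1.960 + 0.842)² × 16/4² = 15.7, i.e. 16 per arm. The stated 26 corresponds to 95% power on these inputs. That is a separate matter; 26 is taken here as the planned number of completers.

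**Variance of one woman's t2–t4 mean (V), and its covariance with the pre-allocation score (c).**
- Equal: V = 16(1 + 2ρ)/3; c = 16ρ.
- Decaying: V = 16(3 + 4ρ + 2ρ²)/9; c = 16(ρ + ρ² + ρ³)/3.

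**Adjusted variance.** With a known slope it is Va = V − c²/16. The slope must be estimated from 52 women, which multiplies the variance by 1 + 1/48 = 1.021. SE = √(2 × variance/26). Half-widths use t with 50 df (2.009) unadjusted and 49 df (2.010) adjusted.

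| Structure, ρ | V | Va × 1.021 | Ratio | Half-width, unadjusted → adjusted | Extra women needed unadjusted |
|---|---|---|---|---|---|
| Equal 0.3 | 8.53 | 7.24 | 85% | 1.63 → 1.50 | 18% |
| Equal 0.5 | 10.67 | 6.81 | 64% | 1.82 → 1.45 | 57% |
| Equal 0.7 | 12.80 | 5.06 | 40% | 1.99 → 1.25 | 153% |
| Decay 0.3 | 7.79 | 7.63 | 98% | 1.55 → 1.54 | 2% |
| Decay 0.5 | 9.78 | 8.59 | 88% | 1.74 → 1.63 | 14% |
| Decay 0.7 | 12.05 | 8.04 | 67% | 1.93 → 1.58 | 50% |

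The last column is V/(Va × 1.021) − 1. Simulating 40,000 trials per setting at 26 per arm gave ratios within about one percentage point of these.

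**t4 alone, decaying correlation.** The correlation with the pre-allocation score is ρ³, so the ratio is (1 − ρ⁶) × 1.021 = 1.02/1.005/0.90. There is a trivial loss at 0.3 and 0.5, and a gain only at 0.7.

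**Power at 4 points, unadjusted.** For the t2–t4 mean (noncentral t) it is 99.8/99.1/97.7% (equal) or 99.9/99.5/98.3% (decaying).

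**Bias if t1 is used as baseline and has been shifted by knowledge of the arm.** Taking t1 in the baseline position, the adjustment slope is c/16. Each point of shift therefore moves the estimate by 0.30/0.50/0.70 point (equal) or 0.14/0.29/0.51 (decaying). The size of any shift is unknown; one point is only a unit.

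**Chance imbalance before allocation.** SE = 4√(2/26) = 1.11 points. A difference of at least 1 point arises in about 37% of such trials, and of at least 2 points in about 7%. This belongs to the same sampling uncertainty that the half-widths already express and is not an addition to it.

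**EQ-5D.** The variance ratios do not depend on the SD, so they hold for the same contrast if the correlations are the same.

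**The case against.** The strongest reply is that the absence rests largely on missing marks in a figure that is visibly incomplete. Its personal-costs row has no mark, although the text plans cost collection at the trimester appointments. Its header row is shifted, and t5 appears twice. This stands as a reason for less than full confidence. It does not overturn the reading: the GAD-7 and EQ-5D marks line up with the consultations, after consent and allocation, and Chart 1 independently omits both forms.

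Second, the bias is hypothetical. Nothing says that t1 will be the baseline, and its place among the visits suggests a follow-up measure. GAD-7 asks about the past two weeks, so a form completed near allocation would mostly cover time before it. This weakens the worry, but a recall period does not prevent reporting from being coloured by knowledge of the arm. The bias is therefore stated only conditionally.

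Third, the gain from adjustment depends on assumed correlations and on a contrast the plan does not name, and it can vanish for a late single visit. This is correct, and the table and the t4 result show it.

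Fourth, the Analysis plan already permits baseline adjustment. It does, but permission is of little use for a score that is never collected.

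**Conclusion.** The point holds, with moderate to high confidence. No pre-allocation GAD-7 or EQ-5D is scheduled, and the role of t1 is unstated. The cost is precision: from almost nothing (decaying correlation, ρ = 0.3) to a variance 2.5 times as large as it need be (equal correlation, ρ = 0.7) for the t2–t4 mean. These figures rest on SD 4, 26 completers per arm and the assumed correlations.

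A reader might infer three stronger things that the documents do not support:
- That the primary comparison is invalid without a baseline. Randomisation keeps the unadjusted comparison valid.
- That the trial is underpowered for this reason. Power at the planned 4 points exceeds 80% in every case examined.
- That the estimate is biased. Bias arises only if t1 is used as baseline and knowledge of the arm has shifted it, and the plan establishes neither.

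This is an improvement that should be made. It is not a flaw that undermines the trial.

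**What to change.** Have the first GAD-7 and EQ-5D completed after consent and before the envelope is opened, alongside Chart 1, and show this in Figure 2. Prespecify the pre-allocation GAD-7 as a covariate in the primary model and the pre-allocation EQ-5D as a covariate in the cost-utility regressions. State which later visits are outcomes and, if t1 is kept, what it is for.

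The cost is a schedule edit and a few lines in the Analysis plan, with no extra women. If the existing t1 forms are moved forward, there is no separate post-allocation first-trimester score. If t1 is also kept as an outcome, each woman answers 12 more items (7 + 5), in a study whose Discussion already names the number of evaluations as a difficulty. If the correlation proves very low, adjustment costs about 2% in variance. Trial status says recruitment follows ethics approval, so on the document's own account the change can still be made. A pre-allocation score cannot be recovered later.
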